1.0 STUDY OVERVIEW

Study Title: Adapting the SHARE for Dementia Early-Stage Dyadic Intervention: A Stage 1 Pilot Study with African American Families

This pilot project is funded as part of the Roybal Centers, by the National Institute on Aging (NIA). The project involves culturally tailoring the SHARE program for Black/African American PLWDs and their CGs in the early to moderate stages of dementia. The goal of this study is to support conversations around care values and preferences in Black/African American dyads living with a dementia diagnosis in an effort to address disparities.

This two-year study is divided into Stage 1A and Stage 1B, involving four main aims:

Stage 1A; Culturally tailor SHARE for African American dyads

Aim 1: Review SHARE for Dementia materials with an Advisory Committee (AC; 6-10 African Americans with lived experience and experts) to identify distinct needs of African American care dyads and culturally adapt SHARE using this input. Deliverables: Develop SHARE V1 Culturally tailored V1 SHARE Counselor Manual, V1 SHARE Guide for Families, and V1 SHARE Counselor training

Aim 2: Conduct focus groups with African American care dyads (n=2 groups; n=10 dyads total, or until saturation) and community service provider staff (n= 2 groups; n=10, or until saturation) to identify strengths and limitations of the V1 SHARE materials, procedures, and protocols. Deliverables: SHARE for African Americans (Version 2;V2); Culturally tailored V2 SHARE Counselor Manual, V2 SHARE Guide for Families, and V2 SHARE Counselor training

Stage 1B; Conduct a pilot RCT of the adapted SHARE versus usual care

Aim 3: Train SHARE counselors (n=20) to implement V2 of SHARE.

Aim 4: Examine: a) the acceptability and feasibility and; 2) preliminary efficacy of the culturally adapted V2 of SHARE in a fully powered trial with 120 African American care dyads.

[figure not shown]

3.0 STUDY FLOW

4.0 INFORMED CONSENT

During the screening phone call, researchers will explain the study and consent process and ask the respondent to verbally consent after reading the consent form. If a participant does not consent, they will not be enrolled. All consent forms will include the following information in clear and understandable language: (1) participants agree in an entirely voluntary manner to participate in the specific research project, the purpose of which is stated, as well as the anticipated sources (i.e., questionnaires), use, and benefits of the data; and (2) participants understand that they are free to decline to participate or to withdraw their participation at any time; (3) participants understand that their participation or refusal in this research project in no way affects the availability or quality of health and social services that they are currently receiving or might wish to receive in the future; and (4) participants understand that all information in the research project will be kept confidential according to strict procedures and that results will be reported in an aggregate manner. At each phase of the consent process, users, staff, and persons with dementia will be informed of the voluntary nature of their participation. Once consented, a physical copy of the verbal consent will be sent to all participants for their records as part of the enrollment packet.

4.1 HIPAA Authorization

The Research Screener will explain to the dyad that the research team will collect the PWD's protected health information (PHI) for use in this study, as specified in the consent form they have signed. Participant information will only be accessed as needed to collect study-relevant data, including the following: diagnoses, medications, pertinent health history, demographics, such as age, race/ethnicity, date of birth, sex, and education level.

5.0 RECRUITMENT AND RETENTION

5.1 Participant Recruitment

Our plan is to recruit 120 Black and African American dementia dyads. The Benjamin Rose Institute on Aging in Cleveland, OH will serve as the primary recruitment site. We will recruit locally in Cleveland, OH and surrounding areas through Benjamin Rose Institute on Aging's Rose Centers for Aging Well, which houses our home delivered meals program; our Empower and Strengthening Ohio's People financial counselor program, our Eldercare Services Institute that offers social work and mental health services, and our Margaret Wagner Apartment buildings. We will also utilize Benjamin Rose's multitude of community connections through local churches, various community-based agencies, and large healthcare systems. The National Caucus and Center for Black Aging, Inc. (NCBA) will also serve as a recruitment site for the clinical trial. NCBA is the preeminent national organization on issues impacting minority citizens aged 55 and older. The Cleveland chapter is located in the Fairhill Center for Aging and houses the Senior Community Service Employment Program (SCSEP), a paid community service and work-based training program that serves a large percentage of AA families (see letters of support).

Project Consultant, [name], will assist in recruiting dyads through Emory University Goizueta Alzheimer's Disease Research Center Minority Engagement Core and Emory Healthcare Integrated Memory Care Clinic. Using the church connections of the Emory University Goizueta Alzheimer's Disease Research Center Minority Engagement Core and Georgia State University Dementia Friendly Faith Village Community Program, we will advertise in church bulletins. Church leaders and congregation members may also refer a dyad who may be

interested in the study. Through the Emory Healthcare Integrated Memory Care Clinic, we will work with clinicians to identify potentially eligible participants. In addition to the local recruitment, we will use discussion boards of national organizations (American Psychiatric Nurses Association and Gerontological Society of America) and community connections of social and professional organizations (Zeta Phi Beta Sorority, Incorporated). The members of these organizations can also refer dyads who may be interested in the study. If additional dementia dyads are needed, we will use snowball recruitment, asking enrolled caregivers to refer other dementia dyads like themselves to participate.

Enrollment packets will be mailed to eligible and enrolled care dyad participants individually. Included in each care partner's enrollment packet will be a cover letter, a study flyer, two copies of the verbal consent form (to be retained for the person's records), and a Microsoft Teams instructional guide to prepare for remote sessions. The cover letter, consent form, and flyer will have phone numbers, addresses, and email addresses for the PI and the designated IRB. The person will be invited to contact any of these individuals if they have any questions. The consent form will include detailed information about what participation in the study entails for residents. It will also list all of the potential risks of the study and ways in which researchers will be protecting against the risks. Potential benefits will also be described. In all recruitment materials, it will be made clear that participation in this study is voluntary, and that participants can stop participating at any time.

Recruitment will continue until we reach the target sample size (N=120 dyads) for Aim 4. If the recruitment strategies do not obtain the desired sample, we will use social media (e.g., Facebook, twitter). We will also post/distribute flyers describing the study and contact information in private geriatrician offices, senior centers, libraries, and other public venues so that caregivers can contact the study office for further information and enrollment.

Recruit dementia care professionals to be trained in V2 of the adapted SHARE (i.e., adapted for African American dyads). Direct service staff from various community-based service organizations or clinic-based settings will be trained to conduct SHARE (n=20). The benefit of working with a broad group of providers is that they will have varying levels of prior training and experience working with African American families. We anticipate that few staff will be trained specifically in dementia-related issues that emphasize working with care dyads. Each trainee will be asked to complete the SHARE online training course within a two week-long period of time. Three additional hour-long webinars will be presented to SHARE Counselor trainees that will be focused on the specific cultural adaptations determined by the Advisory Council and Focus Groups in the Stage 1A study.

5.2 Participant Retention

Missing data and attrition are expected. We conservatively estimated missing data of 10% of the entire sample and potential attrition of 20%. Thus, we are recruiting 120 dementia dyads for Aim 4 to yield a minimum final sample of around 100 AA dementia dyads. To promote retention between data collections, we will send "thank you" notes, birthday cards, and holiday greetings. Members of the research team will establish a positive rapport and good working relationships with participants to reinforce participation throughout the study period. In addition, participants will receive a \$25 honorarium for participating in data collection in each data point (baseline and follow-up).

6.0 SCREENING AND ELIGIBILITY CRITERIA

6.1 Screening

1. Pre-Screening will begin over the telephone with a Research Screener contacting the care partner that was referred. The Research Screener will ask a series of questions to determine if basic eligibility criteria are met:
 - a. One or both care partners identify as non-Latinx Black or African American
 - b. One care partner reports signs and symptoms of mild to moderate dementia memory concerns (e.g., Alzheimer's disease, vascular dementia, mild cognitive impairment, etc.) and one care partner identifies with being the person who is or will provide assistance to them in the future
 - c. Both care partners live in the community (e.g., home or apartment) and not in an institutionalized setting (e.g., assisted living or nursing home)
 - d. At least one care partner has a computer and a wifi connection they can use to participate in the study

Once the dyad is pre-screened for eligibility:

2. Full screening is conducted by the Research Screener to make a final eligibility determination whether the PWD and CG meet the following inclusion / exclusion criteria:
 - a. PWD is 50+ and CG is 18+
 - b. Both care partners able to read and speak English
 - c. PWD is diagnosed with dementia (of any type) or has symptoms consistent with mild to moderate dementia through CG report on the Dementia Severity Rating Scale.
 - d. Neither care partner has a terminal illness diagnosis and is receiving hospice care
3. The Montreal Cognitive Assessment (MoCA) will be conducted by the Research Screener by interviewing the PWD.
 - a. Eligibility will be determined by the DRS; the MoCA will be administered to the PWD during screening if the dyad screens in based on DRS results

6.2 Screening Log

After completing the screening process, the Research Screener will enter data into the Screening Log. The Screening Log will be digital in nature (an Excel spreadsheet) include the following information: the dyad's initials, identification number (screening number), age, gender, race, ethnicity, screening date, and eligibility status. (e.g., eligible for study participation and date enrolled; ineligible for study participation and reason; refused consent and reason). The file will be saved on the Benjamin Rose servers. Enrollment and screen failure data will be added into the respective CROMS databases.

6.3 Eligibility Criteria

Inclusion Criteria

PWD

PWD must reside in a community setting, such as a home or apartment, be 50+ years old, diagnosed with any type of dementia or report symptoms consistent with dementia, speak and read English.

CG

CG must identify as non-Latinx Black or African American or be caring for someone who is non-Latinx Black or African American, be at least 18 years old, speak and read English, and is a person who will have responsibility for helping with the PWD's care.

Exclusion Criteria

Dyad will be excluded if one or both care partners refuse to participate, either are bed confined, unable to communicate verbally, have serious visual or hearing impairments and if the PWD scores below moderate on the Dementia Severity Rating Scale as reported by the CG.

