8.0 STUDY MEASUREMENTS AND PROCEDURES

See section 3.0 Study Flow for details on study procedures between screening and study completion. The below tables document the study timeline and schedule divided between PWD and CG study protocols.

PWD Timeline and Schedule				
Interview/Data Collection	Screening (1 week)	Baseline (within 2 weeks after screening)	Treatment or Control Period (Tx; 8-10 weeks; C: single session)	Follow-Up (within 2 weeks of completion of intervention period)
Informed Consent Form	X			
Confirm Age 50+ (Screening)	X			

Confirm Read & Speak English (Screening)	X			
Confirm Dementia Symptoms or Diagnosis (Montreal Cognitive Assessment; MOCA)	X			
Confirm Exclusion Criteria Do Not Apply	X			
Enrollment (if eligible)	X			
Service Availability Measure (SAM)		X		X
Care Values Scale		X		X
Preferences for Care Tasks Scale		X		X
Dyadic Relationship Scale (DRS)		X		X
Personal and Instrumental Activities of Daily Living (PADL & IADL)		X		X
Emotional-Intimacy Disruptive Behavior Scale (EIDBS)		X		X
Dementia Quality of Life +/- Affect		X		X
Center for Epidemiological Studies Depression Scale (CES-D)		X		X
Leisure & Healthy Behaviors		X		X
Quality of Life – AD (QoL-AD)		X		X
SHARE Care Plan (Treatment ONLY)			X	
Resource List (Control ONLY)			X	
Post-Session Evaluation (1 – Control; up to 6 – Treatment)			X	
Treatment Fidelity / Acceptability Measures			X	
Satisfaction Questions				X

CG Timeline and Schedule				
Interview/Data Collection	Screening (1 week)	Baseline (within 2 weeks after screening)	Treatment or Control Period (Tx; 8-10 weeks; C: single session)	Follow-Up (within 2 weeks of completion of intervention period)
Informed Consent Form	X			
Confirm Age 50+	X			

(Screening)				
Confirm Read & Speak English (Screening)	X			
Confirm Dementia Symptoms or Diagnosis (Dementia Rating Scale)	X			
Confirm Exclusion Criteria Do Not Apply	X			
Enrollment (if eligible)	X			
Service Availability Measure (SAM)		X		X
Care Values Scale		X		X
Preferences for Care Tasks Scale		X		X
Dyadic Relationship Scale (DRS)		X		X
Personal and Instrumental Activities of Daily Living (PADL & IADL)		X		X
Personal and Instrumental Activities of Daily Living (PADL & IADL)		X		X
Emotional-Intimacy Disruptive Behavior Scale (EIDBS)		X		X
Dementia Quality of Life +/- Affect		X		X
Center for Epidemiological Studies Depression Scale (CES-D)		X		X
Stress in Providing Care		X		X
Leisure & Healthy Behaviors		X		X
Quality of Life – AD (QoL-AD)		X		X

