15.0 DATA COLLECTION AND STUDY FORMS

Below is a list of documents that will be used in the study:

Screening

- Dementia Rating Scale (DRS)
- Montreal Cognitive Assessment (MoCA)

DYAD

Baseline Assessments

- Service Availability Measure
- Care Values Scale (CVS)
- Preferences for Care Tasks Scale (PCTS)
- Dyadic Relationship Scale (DRS)
- Personal and Instrumental Activities of Daily Living (PADL & IADL)
- Emotional-Intimacy Disruptive Behavior Scale (EIDBS)
- Dementia Quality of Life +/- Affect
- Center for Epidemiological Studies Depression Scale (CES-D)
- Stress in Providing Care
- Leisure & Healthy Behaviors
- Quality of Life – AD (QoL-AD)

Follow Up Assessments

- Service Availability Measure
- Care Values Scale (CVS)
- Preferences for Care Tasks Scale (PCTS)

- Dyadic Relationship Scale (DRS)
- Personal and Instrumental Activities of Daily Living (PADL & IADL)
- Emotional-Intimacy Disruptive Behavior Scale (EIDBS)
- Dementia Quality of Life +/- Affect
- Center for Epidemiological Studies Depression Scale (CES-D)
- Stress in Providing Care
- Leisure & Healthy Behaviors
- Quality of Life – AD (QoL-AD)
- Satisfaction with SHARE/Control Sessions

Counselors

- Post Session Evaluations

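### The section 6.3 severity exclusion, as worded, removes the mild cases that sections 1.0 and 6.1 set out to recruit; the caregiver schedule also shows the wrong minimum age

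*Protocol*

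**What the plan says.** Four statements in the protocol bear on dementia severity.

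- Section 1.0 describes the target population as Black/African American persons living with dementia and "their CGs in the early to moderate stages of dementia". The study title calls SHARE an early-stage intervention.
- Section 6.1, item 1b (pre-screening): "One care partner reports signs and symptoms of mild to moderate dementia memory concerns". Mild cognitive impairment is among the examples.
- Section 6.1, item 2c (full screening): "PWD is diagnosed with dementia (of any type) or has symptoms consistent with mild to moderate dementia through CG report". The instrument named for this is the Dementia Severity Rating Scale.
- Section 6.3 (exclusion): the dyad is excluded "if the PWD scores below moderate on the Dementia Severity Rating Scale as reported by the CG".

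Item 3a of section 6.1 adds: "Eligibility will be determined by the DRS". The scale has one name in 6.1 and 6.3 (Dementia Severity Rating Scale) and another in the caregiver (CG) schedule of 8.0 and the form list of 15.0 (Dementia Rating Scale). Sections 8.0 and 15.0 also use DRS for the Dyadic Relationship Scale, an outcome measure.

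On age, 6.1 item 2a and 6.3 both set the CG minimum at 18. The CG schedule in 8.0 has a screening row reading "Confirm Age 50" followed by a plus sign, and no row for 18 or over.

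**The concern.** Items 2c and 6.3 use the same scale, the same informant and the same screening step, yet they treat a mild PWD in opposite ways. Two screeners could decide differently on the same dyad, depending on the section each one follows. If both sections are applied as written, the early-stage part of the intended population is lost and moderate cases remain.

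The conflict also reaches the trial's records. Section 6.2 requires the screening log to give a reason for ineligibility, and section 14.0 makes enrolment of an ineligible participant a reportable deviation. Under the present text an enrolled mild PWD complies with 6.1 and is arguably a deviation under 6.3. Mild dyads turned away cannot be recovered later.

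The CG age row is a smaller matter. A screener working from the schedule could turn away caregivers aged 18 to 49 whom both criteria sections admit.

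**Working it through.** The protocol states no figure to reproduce, so the check is a logical one. Cross three severity levels (mild, moderate, severe) with the two entry routes in item 2c (diagnosis, symptoms). Section 6.1 admits a PWD who satisfies both 1b and 2c. Then apply the 6.3 exclusion under each reading of *below*.

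| Severity, route | 6.1 (1b and 2c) | 6.3 read literally | 6.3 with *below* meaning *worse than* |
|---|---|---|---|
| Mild, diagnosis | admits | excludes | keeps |
| Mild, symptoms | admits | excludes | keeps |
| Moderate, diagnosis | admits | keeps | keeps |
| Moderate, symptoms | admits | keeps | keeps |
| Severe, diagnosis | fails 1b (by report); passes 2c | not excluded | excludes |
| Severe, symptoms | fails 1b and 2c | not excluded | excludes |

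**Counts**

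- Admitted by 6.1: 4 of 6.
- Left after 6.3 read literally: 4 − 2 = 2, moderate only.
- Left if *below* means *worse than*: 4 − 0 = 4, which agrees with 6.1 and 1.0.

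**Diagnosis route.** The table applies the 6.3 exclusion to both routes, because its wording has no route limit. Item 2c sets no severity limit for a diagnosed PWD, and item 3a does not say outright whether the scale binds that route. If it did not, the literal rule would remove only the mild/symptoms cell, leaving 4 − 1 = 3. The contradiction with 2c remains in that case too.

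**Upper end.** Read literally, the only scored severity exclusion points to the low side. Severe cases are then limited by the reported item 1b, by the mild-to-moderate band on the symptom route of 2c, and by the bed-confined and non-verbal exclusions. No scored limit applies to a severe PWD who enters by diagnosis.

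**Tally.** Three statements include mild or early-stage PWDs (1.0, 6.1 item 1b, 6.1 item 2c). One excludes them (6.3).

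**CG age.** Two statements say 18 or over (6.1 item 2a and 6.3) and one schedule row says 50 or over. Taken literally, ages 18 to 49 pass the criteria and fail the schedule.

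**The case against.** The best defence is that *below moderate* is loose wording for *worse than moderate*. The context supports this. The neighbouring exclusions in 6.3 (bed confined, unable to communicate verbally, serious visual or hearing impairment) are all incapacities, and a severe-dementia exclusion fits that list better than a mild one. The title says early-stage, and item 1b names mild cognitive impairment. Item 2 of 6.1 is the final eligibility determination and says mild to moderate, so a screener who follows it has a clear instruction. This may well be what was intended. It explains the error without removing it: the exclusion works only if read against its plain words, and 6.3's own inclusion text gives no severity band from which to infer the direction.

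The Study Flow content under section 3.0 was not available for this review, so a cut-off may be stated there. That limit stands, but a cut-off elsewhere would not change the contradictory words in 6.3.

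On the diagnosis route, it is fair to say that the 6.3 exclusion and item 3a are unqualified and that the CG schedule row links the scale to both symptoms and diagnosis. The likelier reading is that the scale binds everyone. The point is therefore one to confirm, not a second contradiction.

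The CG age row may mean that the caregiver confirms the PWD's age, since a nearby row concerns the PWD's dementia. If so, the schedule has no check of the caregiver's own age. The difference in scale names, taken alone, is editorial.

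Finally, the cell counts describe the rule and not the enrolment. That is correct, and no enrolment effect is claimed.

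**Conclusion.** The point holds. As worded, the 6.3 exclusion contradicts 6.1 and 1.0 and, if followed, removes both mild combinations among the four that 6.1 admits (one of the four if the scale does not bind diagnosed PWDs). Moderate cases are in target under every statement, so the harm is the loss of the early-stage group and inconsistent screening decisions about it. The conclusion rests on the ordinary meaning of *below* on a severity scale and on the text available for review, which gives no score direction or cut-off. The protocol reports no severity or age mix, so no proportion of the 120 dyads can be given. The CG age mismatch is real but secondary.

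**What to change.** 1. Reword the severity exclusion in 6.3 so that it agrees with the population in 6.1 and 1.0, and state the score direction and score range on the named scale.
2. Have the investigator confirm whether that range also applies to PWDs who enter by diagnosis, and say so in both 2c and 6.3.
3. In the CG schedule of 8.0, change the age row to 18 or over, or label it as the PWD's age and add a row for the caregiver's own minimum of 18.
4. Use one name for the eligibility scale in 6.1, 6.3, 8.0 and 15.0, with an abbreviation distinct from that of the Dyadic Relationship Scale.

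The cost is limited to protocol wording and the screening forms. No procedure, visit or measure is added.

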7.0 STUDY INTERVENTION

A total of 120 dyads will participate in the intervention. A Randomized Control Trial (RCT) will be conducted (with 60 in the control group and 60 in the treatment group).

The study will follow Barrera's Stages of Cultural Adaptation: 1. Information Gathering, 2. Preliminary Adaptation Design, 3. Preliminary Adaptation Test 4. Adaptation Refinement, 5. Cultural Adaptation Trial. See Figure 1. Below for an outline of how this model fits in with Stage 1A and Stage 1B.

The Stress Process Model (SPM) will also be applied. The revised domains of the SPM will incorporate: 1) Background Characteristics, 2) Primary Objective Stressors, 3) Targeted mechanisms of behavior change after receiving the adapted SHARE intervention, 4) Primary and Secondary Subjective Stressors, and 5) Psychosocial Well-Being Outcomes. See Figure 2. Below for an Overview of how these domains tie into the study and anticipated results.

Figure 1. Barrera's Stages of Cultural Adaptation

[figure not shown]
[figure not shown]

Figure 2. Stress Process Model

